#### **OBJECTIVES OF THE STUDY**

The purpose of this study is to evaluate clinical and radiological parameters of 5 mm short implants (GS) compared to longer implants (GL) (10 mm) placed in sinus-grafted sites.

Null Hypothesis (H0): There are no statistically significant clinical or radiographic outcome differences between the two groups, GS and GL.

Alternative Hypothesis (H1): There are statistically significant clinical or radiographic outcome differences between the two groups, GS and GL.

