#### Primary and secondary endpoints

Primary endpoint: Comparing mesial-distal (M-D) bone loss between the two groups (Radiologic outcome)

Secondary endpoints: Clinical outcomes and Patient reporting outcomes

- 1. Determine the survival rate and success rate of the Group Short (GS) and Group Long (GL) group.
- 2. Compare incidence and types of surgical and prosthetic complications between groups
- 3. Compare the number of sites with bleeding on probing (BOP)
- 4. Compare the cost of both procedures and the cost of the prosthetic complications
- 5. Compare the probing pocket depth (PPD)
- 6. Determine the pain after treatment: Visual analog score (VAS)
- 7. Compare patient satisfaction
- 8. Compare surgical time

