#### **STUDY PROCEDURES**

#### **Clinical measurements**

1) The following measurements will be taken for each treated implant by a blinded, calibrated examiner at the implant placement (surgery V2), at the time of prosthetic placement (5-month postop V6), 12-month follow-up (V8), and 24-month follow-up (V10).

- Marginal bone level (MBL): It will be calculated based on standardized radiographs using registered bite-block with a Rinn (Dentsply Rinn, Elgin, IL, USA) film holder and expressed as the distance from the implant shoulder to the most coronal bone-to-implant contact (BIC) on the mesial and distal side of the implant. The mean values will be calculated for each implant at the time of implant placement, at the time of prosthetic placement (5-month post-op V6), 12-month follow-up (V8), and at 24-month follow-up (V10). In the case that the bone levels around the study implants are hidden or difficult to read, new radiographs will be taken. Peri-implant marginal bone levels will be measured using the ImageJ software\* (ImageJ, U. S. National Institutes of Health, Bethesda, Maryland, USA) (Schneider et al., 2012). The software will be calibrated for every single image using the known implant length or the length of the implant collar. Measurements of the mesial and distal bone crest level adjacent to each implant will be rounded to the nearest 0.1 mm. Implants with bone up to the coronal margin of the implant collar will be given a value of zero. Mesial and distal measurements of each implant are averaged, and a mean calculated at patient level and then at group level.
- PPD and BOP: It will be assessed at 4 sites per implant (mesial, distal, buccal, and palatal) with a measurement stent using a periodontal probe (UNC, Hu-Friedy, Chicago, IL, USA). PPD are measured from the distance of the mucosal margin to the bottom of the probable pocket in mm. BOP is recorded using the following scoring method: 0) no bleeding 1) an isolated bleeding spot is visible, 2) blood forms a confluent red line on margin, and 3) heavy or profuse bleeding.
- Plaque: The level of oral hygiene will be evaluated using the Modified gingival index (Lobene et al., 1986) (Scores 1-4).

0 = Absence of inflammation

1 = Mild inflammation or with slight changes in color and texture but not in all portions of gingival marginal or papillary

2 = Mild inflammation, such as the preceding criteria, in all portions of gingival marginal or papillary

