#### Intra-operatory measurements

- Subjective evaluation of the bone type (Lekholm & Zarb 1985) during implant site preparation will be performed by the surgeon.
  - Type 1: Almost entirely comprised of homogeneous compact bone

- Type 2: thick layer of compact bone surrounding a core of dense trabecular bone
- Type 3: thin layer of cortical bone surrounding a core of dense trabecular bone
- Type 4: Thin layer of cortical bone surrounding a core of low-density trabecular bone coupled with the surgeon's tactile perception
- Thickness of soft tissues will be measured with a 1.0-mm marked periodontal probe (UNC, Hu-Friedy, Chicago, IL, USA) on the top of bone crest in the center of future implant placement. This will ensure direct visibility of mucosal thickness during measurement.
- Patient phenotype: Classification of the patient's phenotype will be thin, medium, thick, or very thick by using the Colorvue biotype probe (Hu-Friedy).
- Chair time of the surgical procedure will be recorded from the end of local anesthesia until the completion of sutures.
- The time required for placement of one single implant, with both treatments (short implants and sinus floor elevation with placement of longer implants) will be calculated as follows: the time required for the entire surgical procedure (from anesthesia to sutures) will be assessed for each patient and divided by the number of installed fixtures. The ratio of the time required for placement of a single short implant to the time required for a sinus floor elevation procedure in combination with a longer implant will be calculated and expressed as a percentage.
- A wireless magnetic-based Osstell Mentor RF Analyzer (Ostell USA, Linthicum, MD, USA) will be used to assess primary implant stability. The designated transducer (SmartPeg) will be hand-tightened per the manufacturer's instructions to the fixture. ISQ values will be taken immediately after implant placement and measured in triplicate and averaged to yield the mean baseline ISQ value for each implant.

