#### STATISTICAL CONSIDERATIONS

The study will be powered to detect a minimum clinically significant difference in bone loss of 0.5 mm using  $\alpha = 0.05$ , a power  $(1 - \beta) = 80\%$ . Considering possible dropouts, the number of patients will also be increased by 10% for each arm. On the basis of this data, the minimum needed number of patients to be enrolled in this study is 17 with for the test group (GS) and 17 for the control group (GL). Mean values, standard deviations, and medians will be calculated for the clinical parameters. The association between crown-implant ratio and final bone loss as well as prosthetic complications will be examined. Changes of the parameters over time within the two groups as well as differences between groups will be analyzed using repeated measure of analysis of variance (ANOVA).

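### The plan describes no repeat reading of the primary bone level and no within-reader repeatability; reading each film twice would be an inexpensive, optional gain in precision

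*Combined protocol and SAP*

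**What the plan says.** The primary endpoint is given under Primary and secondary endpoints as "Comparing mesial-distal (M-D) bone loss between the two groups (Radiologic outcome").

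The Clinical measurements section explains how marginal bone level (MBL) is obtained. A blinded, calibrated examiner reads standardized bite-block films in ImageJ, with the scale set on each image from a known implant or collar length. Then: "Measurements of the mesial and distal bone crest level adjacent to each implant will be rounded to the nearest 0.1 mm". Averaging runs over mesial and distal sides, then the patient, then the group. An implant with bone up to the top of its collar is scored zero. Films that are hard to read are retaken. Nothing is said about a second reading, a second reader or the examiner's repeatability.

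Elsewhere the protocol does specify replication. Under Intra-operatory measurements, implant stability (ISQ) at placement is "measured in triplicate and averaged to yield the mean baseline ISQ value for each implant". ISQ is neither the primary endpoint nor one of the eight listed secondary endpoints.

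Statistical Considerations says the trial is "powered to detect a minimum clinically significant difference in bone loss of 0.5 mm", with 5% alpha and 80% power, and gives a minimum of 17 per arm. Study Design allows up to 50 patients, half per arm, and Participants says 50 will be recruited.

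**The concern.** Bone loss is the difference between two films, so the random error of marking the bone crest on both films enters each patient's value. That error widens the SD of the primary outcome and costs power. Part of it can be averaged out by re-reading films that the trial takes anyway, with no new patients, visits or exposure.

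There is a second use for repeat readings. Peri-implantitis is defined as detectable bone loss beyond initial remodeling, with no threshold in millimetres. What is detectable depends on how well the reader reproduces a reading, and the plan does not measure this. The definition also bears on a secondary endpoint: implant success requires the absence of any biological complication, and peri-implantitis is listed among these under Implant Related Risks.

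**Working it through.** **The plan's own figure.** Inputs: difference 0.5 mm, alpha 0.05, power 80%, 10% dropout allowance. The test is taken as two-sided because the alternative hypothesis has no direction. The text says "On the basis of this data, the minimum needed number of patients to be enrolled in this study is 17" per arm but shows no SD, so 17 cannot be reproduced from the stated inputs. Working backwards by the normal approximation, n = 2(1.96 + 0.84)² × SD² / 0.5². An SD of 0.48 mm gives 14.5, rounded up to 15, and 15 / 0.9 = 16.7, rounded up to 17. The SDs that fit are 0.473–0.488 mm (normal approximation) or 0.455–0.471 mm (t-test). If 17 is the number before inflation, they are 0.505–0.520 or 0.489–0.504 mm.

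**Assumptions for the check.** The SD of bone loss with single readings is 0.5 mm, a round value close to those ranges. The marking SD per side per film, s, is 0.1, 0.2 or 0.3 mm; the documents give no value. Errors are independent between readings, sides and films. The analysis is a two-sided t-test on a two-film change, which is simpler than the planned repeated-measures ANOVA.

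**Error model.** The mesial–distal mean on one film has marking variance s²/2. The difference of two films has s²/2 + s²/2 = s². With two readings averaged this becomes s²/2, so the saving is s²/2 out of 0.25:

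- s = 0.1: 0.005 / 0.25 = 2%; new SD 0.495 mm
- s = 0.2: 0.020 / 0.25 = 8%; new SD 0.480 mm
- s = 0.3: 0.045 / 0.25 = 18%; new SD 0.453 mm

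**Power for a 0.5 mm difference (t-test).**

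| Analysed per arm | One reading | Two, s = 0.1 | Two, s = 0.2 | Two, s = 0.3 |
|---|---|---|---|---|
| 15 (minimum 17, less dropout) | 75.3% | 76.1% | 78.7% | 83.1% |
| 22 (25, less about 10%) | 90.0% | 90.5% | 92.2% | 94.7% |
| 25 (planned 50, no dropout) | 93.4% | 93.8% | 95.1% | 96.9% |

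**Effect of the zero rule.** Where the placement film is scored zero under the collar rule, that film carries little marking error. If this held for every patient, the marking variance of the change would be s²/2 and two readings would save s²/4, or 1% / 4% / 9%. Power at 15 per arm would then reach only 75.7% / 77.0% / 79.1%. The number of implants that qualify is unknown, so 2% / 8% / 18% is the upper case under this model.

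**Rounding.** Rounding to 0.1 mm adds an SD of 0.1 / √12 = 0.029 mm, under 0.5% of the variance. Rounding is not the issue.

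**Individual patients.** With single readings, the 95% noise band for one patient's two-film change is ±1.96s, or ±0.20 / ±0.39 / ±0.59 mm. At the upper value it exceeds the 0.5 mm that the plan calls clinically significant.

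**The case against.** The strongest reply is that the plan already protects this measurement and has power to spare. The films are standardized with a bite-block, the examiner is blinded and calibrated, every image is scaled, unreadable films are retaken and two sides are averaged. At the planned 50 patients, power under these assumptions is already 90% to 93%, and two readings add only about 0.4 to 5 points. This stands, and it limits the size of the point. However, calibration and scaling deal mainly with systematic error, and the averaging of sides is already credited in the formula, so neither takes the place of repeat readings.

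Three stronger readings are tempting, and the documents do not support them.

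- A reader might infer that the protocol prescribes a single reading. It gives no number; single reading is inferred from an averaging chain that has no replicate step.
- A reader might infer from the 75% that the trial misses its 80% target. That figure follows from the assumed SD of 0.5 mm. At 0.463 mm, within the back-solved range, 15 per arm gives 81.5%. The unstated planning SD may also already include single-reading error, in which case the stated power stands and repeat readings add margin.
- A reader might take the ISQ triplicate as a standard that MBL fails. The triplicate is specified only for ISQ at placement; the later ISQ at healing abutment placement has no stated number of repeats. Replicating a device reading sets no rule for films. The contrast shows only that the authors specify replication in one place and not in the other.

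It is also fair to say that a re-read subset would be enough to estimate the within-reader SD. Reading every film twice is needed only for the gain in precision.

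**Conclusion.** The point holds as an optional improvement. The plan describes neither repeat readings of its primary outcome nor any measure of reader repeatability. No bias between arms, contradiction or invalid power statement follows from this.

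The size depends on a marking error that the documents do not give. Near 0.1 mm, the gain is about one point of power or less at any of the sample sizes considered. At 0.2 to 0.3 mm it is about 3 to 8 points at the minimum sample and about 2 to 5 points at 22 to 25 per arm. These figures assume a bone-loss SD of 0.5 mm, independent errors and a two-film t-test, and they shrink where the zero rule applies. Differences in projection between films are not reduced by re-reading. The repeatability figure would be useful even if the gain in power proved negligible.

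**What to change.** In Clinical measurements, under marginal bone level, state that the same blinded, calibrated reader measures the mesial and distal levels on each film twice, in separate sessions, without sight of the first values and with the image rescaled each time. Use the average as the MBL. Report the within-reader SD, and judge detectable bone loss in the peri-implantitis definition against it.

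The cost is reader time only. With four measurement times and two sides, the second round is 34 × 4 × 2 = 272 side-readings at the minimum sample, or 50 × 4 × 2 = 400 at full recruitment. No extra film, visit or staff is needed. The downside is that this effort buys little power if the marking error turns out to be near 0.1 mm.

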concluded that short implants with <8 mm should be used with caution because they present a higher risk of failure as compared to standard-length ( $\geq$ 8mm) implants (Lemos et al., 2016). In a systematic review based on the evaluation of 8 randomized controlled clinical trials (RCTs), the European Academy of Osseointegration (EAO) Consensus Conference in 2015 noted that longer dental implants in the augmented sinus caused a higher number of biological complications, increased morbidity, costs and surgical time. Therefore, shorter dental implants may be the preferred treatment alternative (Thoma et al., 2015). A recent multicenter, randomized, controlled clinical trial found that short implants (6 mm) for single-tooth restorations in the posterior maxilla were a viable solution versus longer implants ( $\geq$ 10mm) in combination with sinus lift. After three years of follow-up and with a residual ridge height of 5–7 mm, no implants were lost in both groups and no statistically significant difference in prosthetic complications were reported (Pohl et al., 2017). All these studies excluded patients with a previous history of periodontitis.

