3 = Moderate, bright surface inflammation, erythema, edema and/or hypertrophy of gingival marginal or papillary

4 = Severe inflammation: erythema, edema and/or marginal gingival hypertrophy of the unit or spontaneous bleeding, papillary, congestion or ulceration.

- Prosthesis failure: Planned prosthesis which could not be placed due to implant failure(s), loss of the prosthesis secondary to implant failure(s), or replacement of the definitive prosthesis for any reason.
- Implant failure: It will be defined as implant mobility (assessed from force applied with two hand instrument), pain, or neuropathy.
- Implant success: It will be defined as 1) Absence of persistent subjective complaints such as pain, foreign body sensation and/or dysesthesia 2) Absence of a peri-implant infection with suppuration 3) Absence of mobility 4) Absence of a continuous radiolucency around the implant and 5) Absence of any biological or prosthetic complications (Buser et al., 2012)
- Peri-implantitis: It will be defined as detectable radiographic bone loss beyond the initial biological bone remodeling.

2) The following measurements will be taken for each treated implant by a blinded, calibrated examiner after implant placement, 12-month follow-up, and 24-month follow-up.

Bone thickness (BT): It will be determined based on CBCT and expressed as the distance from the most coronal bone-implant contact to the outer surface of the buccal plate. The mean values will be calculated for each implant.

3) The following measurements will be taken for each treated implant by a blinded, calibrated examiner at prosthetic placement, 12-month follow-up, and 24-month follow-up.

- Crown to implant ratio: The height of the crowns will be measured on the radiographs from the implant-abutment interface to the most coronal point on the crown. The anatomical crown-to-implant ratio (anatomical C/I ratio) will then be calculated dividing the anatomical crown by the length of the implant.4)
- 4) ISQ (Implant stability quotiant) will be measured at the time of healing abutment placement.

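### A patient whose implant is lost or removed before V10 would drop out of the primary bone-loss comparison, and the plan has no rule for this

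*Combined protocol and SAP*

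**What the plan says.** The Primary and secondary endpoints section makes mesial-distal bone loss between the groups the primary endpoint, without naming a time point. Survival and success rates are secondary.

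Under Clinical measurements, marginal bone level (MBL) is the "distance from the implant shoulder to the most coronal bone-to-implant contact (BIC) on the mesial and distal side of the implant". The two sides are averaged, with a "mean calculated at patient level and then at group level". The section covers two special cases:

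- Best outcome: "Implants with bone up to the coronal margin of the implant collar will be given a value of zero".
- Unreadable films: if bone levels are "hidden or difficult to read, new radiographs will be taken".

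It has no entry for an implant that is no longer in the mouth. Implant failure, a separate item, is "defined as implant mobility (assessed from force applied with two hand instrument), pain, or neuropathy".

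Statistical Considerations says that changes over time and differences between groups "will be analyzed using repeated measure of analysis of variance (ANOVA". No analysis set, missing-data method or sensitivity analysis is given. The sample size is raised by 10% per arm for dropouts. The section on questionnaires asks for the reason for a drop-out to be recorded, and Data Management lets the Principal Investigator exclude subjects after enrolment.

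**The concern.** An implant that has been lost or removed has no shoulder from which to measure. Classical repeated measures ANOVA needs a complete set of visits per patient, so such a patient would leave the primary comparison, including any bone levels already recorded. If lost implants tend to be those with poor bone support, the group mean describes only the better implants in that arm. If the arms lose different numbers, the between-group difference is biased.

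The protocol foresees such losses. Its definition of prosthesis failure includes a crown that cannot be placed, or is lost, because the implant failed, and implant failure heads its list of implant-related risks. Counting survival as a secondary endpoint does not repair the primary comparison. The 10% inflation replaces numbers; it does not correct for which patients are missing.

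The stake is interpretation. The null hypothesis is no difference, and the background suggests that shorter implants may be preferred. A true difference reduced by selective loss could be read as support for the short implant.

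**Working it through.** **Inputs from the documents.** Target difference 0.5 mm, α = 0.05, power 80%, 10% dropout increase, minimum 17 per arm (Statistical Considerations); up to 50 patients, half per group, so 25 per arm (Study Design).

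**Inputs not in the documents.** SD of bone loss, sidedness of the test, and expected rate of implant loss. These are assumed below.

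**Step 1: the plan's own figure.** With two-sided α, n per arm = 2(1.960 + 0.842)² × SD² / 0.5² = 62.8 × SD². At SD 0.48 mm this is 14.5, so 15. Both 15/0.9 = 16.7 and 15 × 1.1 = 16.5 round up to 17. The stated 17 therefore fits an SD of 0.473–0.488 mm by this formula. The t-based calculation gives 15 evaluable for an SD of 0.455–0.471 mm. A one-sided test would imply 0.533–0.550 mm. I use 0.47 mm and check 0.48 mm.

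**Step 2: worst case.** Draw GS bone loss from a normal distribution with mean 0.5 mm above GL and the same SD. Delete the k largest GS values, delete nothing from GL, and apply a two-sided t-test.

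| Per arm | GS implants dropped | Estimate, SD 0.47 | Power, SD 0.47 | Estimate, SD 0.48 | Power, SD 0.48 |
|---|---|---|---|---|---|
| 17 | 0 | 0.50 mm | 85% | 0.50 mm | 84% |
| 17 | 1 | 0.45 mm | 78% | 0.45 mm | 77% |
| 17 | 2 | 0.40 mm | 70% | 0.40 mm | 68% |
| 17 | 3 | 0.36 mm | 61% | 0.36 mm | 58% |
| 25 | 0 | 0.50 mm | 96% | 0.50 mm | 95% |
| 25 | 1 | 0.46 mm | 93% | 0.46 mm | 92% |
| 25 | 2 | 0.43 mm | 90% | 0.43 mm | 88% |
| 25 | 3 | 0.40 mm | 85% | 0.40 mm | 83% |

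Hand check for one loss at 17 per arm: the expected maximum of 17 standard normal values is 1.79, so the GS mean falls by 1.79 × 0.47 / 16 = 0.053 mm, leaving 0.447 mm. The shift is proportional to the SD. Over the implied range of 0.455–0.550 mm, one such loss moves the estimate by 0.051–0.062 mm.

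**Step 3: other loss patterns (SD 0.47 mm).** If the GS losses are random, the estimate stays at 0.50 mm and power at 17 per arm is 81–84% for one to three losses. If the worst k are lost in both arms, the estimate also stays at 0.50 mm. If the worst k are lost in GL only, the shift is equal and opposite: about 0.55, 0.60 and 0.64 mm at 17 per arm.

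**Step 4: chance of any loss in an arm,** 1 − (1 − p)ⁿ, over an assumed range of p:

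| Loss rate p | n = 17 | n = 25 |
|---|---|---|
| 1% | 16% | 22% |
| 3% | 40% | 53% |
| 5% | 58% | 72% |
| 10% | 83% | 93% |

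**The case against.** **Failed implants in general.** A reader might infer that every failed implant lacks a bone level. The protocol's definition does not require removal, so an implant failing for pain or neuropathy, or a mobile one still in place, can be radiographed. The problem is confined to lost or removed implants.

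**Direction.** A reader might infer that losses will fall mostly in GS and that the primary result would favour GS. The background does say that "short implants with <8 mm should be used with caution because they present a higher risk of failure", and GS implants are 5 mm. But the same meta-analysis found no significant difference in survival, and the cited multicentre trial of 6 mm implants against longer implants with sinus lift lost none in either arm over three years. The background also links longer implants in the augmented sinus to more biological complications, and the risk sections list graft failure, infection and sinusitis for procedures used only in GL. GS is a reasonable specific worry, but the documents support only possibly unequal losses.

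**Complete-case handling.** The plan does not state it. It is the usual behaviour of the named method, and another implementation could keep partial records. The silence is itself what needs correcting.

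**Size.** Step 2 is deliberately extreme: it assumes that the lost implants are exactly those with most marginal loss. An implant that never integrates may be lost before loading without marginal loss. Three of 17 is an 18% loss in one arm only, which no figure in the documents supports. At 25 per arm, worst-case power stays above the planned 80%. All of this stands and limits the size of the point. It does not supply the missing rule.

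**Conclusion.** The gap is real and worth fixing. The primary measurement does not exist for a lost or removed implant, and the only named analysis would ordinarily discard that patient. The bias can go either way, is absent if losses are unrelated to bone outcome, and is zero if no implant is lost.

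Even in the worst case, one loss moves the estimate by about 0.05 mm at 17 per arm, or 10% of the 0.5 mm target, and by about 0.04 mm at 25 per arm. Three losses move it by 0.14 mm and 0.10 mm. Power falls below 80% only near the minimum enrolment. These figures rest on a back-solved SD of about 0.47 mm, normal data, a two-sided test, and loss of the worst implants in one arm only. They show what is possible and are not a forecast.

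**What to change.** In Statistical Considerations:

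1. Replace repeated measures ANOVA for MBL with a mixed model for repeated measures that includes all randomised patients and all observed MBL visits. This keeps partial records but assumes data are missing at random. An implant lost before the crown is placed may contribute only its baseline value, so the model alone does not deal with losses that depend on unobserved bone outcome.
2. Add one prespecified sensitivity analysis in which a lost or removed implant receives the worst rank for V10 bone loss, compared by Wilcoxon rank-sum test. Limit the worst rank to lost or removed implants; failed implants still in place keep their measured value. State how patients who miss V10 for other reasons are handled.
3. Report the number of implants lost or removed in each arm beside the MBL result.

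The cost is a few sentences and one extra analysis, with no new data to collect. The rank test gives no difference in mm, so it should stay a sensitivity analysis. The rule should be fixed before allocation is revealed to whoever analyses the data.

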#### **Risk associated with surgery**

Subjects will be assigned to a treatment program by chance. The treatment they receive may prove to be less effective or to have more side effects than the other study treatment(s) or other available treatments. The likelihood that the patient will be assigned a treatment that will be less effective than other study treatments or other available treatments is unknown. Both surgery methods are the standard of care. Mild to moderate pain and swelling is expected for both groups. There is a very low risk of uncontrolled bleeding that may occur with subjects that are in general good health and not taking medications that are classified as a blood-thinner. In some cases, subjects may feel some temporary sensitivity with the teeth next to the implant.

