#### **Implant Related Risks**

- 1) Implant Failure
- 2) Biologic complications such as sinus membrane perforations, persistent bleeding, sinusitis (or acute sinus infection), rupture of sinus membrane, soft tissue (graft) dehiscence, abscess, pus, pain, swelling, peri-implant mucositis (heavily inflamed soft tissue without bone loss), or peri-implantitis (bone loss around the implant).
- 3) Prosthetic complications such as fixed prosthetic device detachment, loosening of abutment screws or healing caps, and fracture of the screw, framework, or occlusal material.

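### Implant failure counts any pain or neuropathy and omits implant loss or removal; survival is undefined, so both faults may carry into secondary endpoint 1 (minor)

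*Combined protocol and SAP*

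**What the plan says.** Secondary endpoint 1, under Primary and secondary endpoints, is "Determine the survival rate and success rate of the Group Short (GS) and Group Long (GL) group". The outcome definitions are under Study Procedures, Clinical measurements.

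- **Failure:** "Implant failure: It will be defined as implant mobility (assessed from force applied with two hand instrument), pain, or neuropathy". No duration, severity or cause is attached to pain or neuropathy, and loss or removal of the implant is not mentioned.
- **Success** has five criteria. The first is "Absence of persistent subjective complaints such as pain, foreign body sensation and/or dysesthesia", the third is absence of mobility, and the fifth is "Absence of any biological or prosthetic complications".
- **Prosthesis failure** covers a prosthesis that cannot be placed, or is lost, because of implant failure. It also covers replacement of the definitive prosthesis for any reason.
- **Survival** is not defined there, in Statistical Considerations or in the appendices.

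The same section says these items are assessed at V2, V6, V8 and V10. Appendix A, the Schedule of Events, marks clinical measurement at V2, V4, V7, V8 and V10. It marks adverse events at every visit from V2 to V10.

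**The concern.** Two definitions in one list apply different thresholds to the same symptom. Brief pain is enough for failure, while success criterion 1 tolerates pain unless it persists. Neuropathy has the same problem: it is unqualified under failure, whereas dysesthesia under success must be persistent.

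The failure rule also leaves out what many readers would take implant failure to mean first, namely that the implant is no longer there. The Background reports an earlier trial of short implants in terms of implants lost, and cites a higher failure risk for implants under 8 mm. Failure and survival are therefore natural questions for a 5 mm implant.

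At stake is the survival part of secondary endpoint 1. With no definition of survival, an analyst could take it as absence of failure and inherit both faults, or as the implant in situ and inherit neither. If this is not settled in advance, the choice could be made after the results are known.

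**Working it through.** The plan states no figure on this point, so the check is mainly a reading of the definitions, with one calculation of scale.

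**Step 1. Apply the written rules to four hypothetical implants.**

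| Implant | Failure rule as written | Success criterion 1 | In situ? |
|---|---|---|---|
| Stable, in place, brief pain at an assessment visit | Failure | Met | Yes |
| Stable, in place, brief neuropathy at an assessment visit | Failure | Met | Yes |
| Stable and painless, then removed | Not a failure | Not breached by its terms | No |
| Mobile, in place, no pain | Failure | Met (criterion 3 is breached) | Yes |

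The first two rows show the mismatch over persistence. The third shows the omission of loss or removal. The fourth shows that failure and absence from the mouth are different events, so survival and failure are not complements even once both are well defined.

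**Step 2. Trace the consequences.**

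- If survival means absence of failure, the implants in rows 1 and 2 count as not surviving although they are in place, and the implant in row 3 counts as surviving although it is gone.
- If survival means in situ, these errors do not reach survival. The failure rule itself still misclassifies.
- Prosthesis failure depends on implant failure. If a stable, painless implant is removed and the crown therefore cannot be placed, the first limb of that definition is not met as written. Brief pain passes through only if it also leads to a prosthesis that is lost or not placed.

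**Step 3. Size of one reclassification.**

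Inputs are arm sizes: 25 per arm (half of the 50 maximum in Study Design) and 17 per arm (the minimum in Statistical Considerations).

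- Shift in an arm's rate per implant = 1/n.
- 1/25 = 4.0 percentage points.
- 1/17 = 5.9 percentage points.

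The documents give no frequency of brief pain at the assessment visits and no frequency of removal of stable, painless implants. The number of implants affected therefore cannot be derived.

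**Step 4. Compare the assessment visits.**

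- Clinical measurements: V2, V6, V8, V10.
- Appendix A, clinical measurement row: V2, V4, V7, V8, V10.
- Only the first list: V6. Only the second: V4 and V7. V4 is the visit for implant exposure surgery.
- Follow-up evaluation visits: implant mobility, one limb of the failure rule, is listed at all eight follow-up visits.

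Which pain could trigger failure depends on which list governs.

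**The case against.** The best opposing case is that little follows in practice. A lost implant will often have been mobile first and so be caught by the existing rule. The Background's use of implants lost points to an in-situ reading of survival, under which neither fault reaches the endpoint. The only scheduled pain assessment is at V3, which is in neither visit list, and V2 is the surgery itself under local anaesthesia. Statistical Considerations names no test specific to survival. All of this stands, and it keeps the point minor. It does not remove the literal mismatch or supply the missing definition.

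A reader might infer more, in four ways that the documents do not support.

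- **That one implant could be classed as both a failure and a success.** Success needs all five criteria. Implant Related Risks lists "abscess, pus, pain, swelling, peri-implant mucositis" among biologic complications, so criterion 5 might exclude any painful implant. That list describes risks and is not an endpoint definition, so it does not settle the matter either way. What can be said is that such an implant passes criterion 1.
- **That ordinary post-operative pain turns many implants into failures.** The protocol does say "Mild to moderate pain and swelling is expected for both groups", but the 2-week visit is in neither list of assessment visits.
- **That the dropout allowance measures the fault.** Statistical Considerations says "Considering possible dropouts, the number of patients will also be increased by 10% for each arm". It gives no rule for counting dropouts in a survival rate. That is a missing detail and says nothing about how pain or removal is classified.
- **That the comparison is biased between arms.** Nothing in the documents shows that either fault would fall more heavily on one arm.

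**Conclusion.** The point holds as a minor defect of definition. The failure rule is broader than success criterion 1 on pain and neuropathy, and silent on loss and removal. Both follow from the text alone, with no outside assumption. Carry-over into survival is conditional: it occurs if survival is read as absence of failure, and the documents neither state nor exclude that reading. Each implant affected is worth 4.0 points at 25 per arm and 5.9 points at 17 per arm, taking every randomised patient as one implant in the denominator. The total effect is unknown. The primary endpoint, mesial-distal bone loss, does not use these definitions and is not affected.

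**What to change.** These are changes to endpoint definitions and do not touch patient care.

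1. Define survival as the implant in situ, neither lost nor removed, up to V10. Report it with the number at risk and separately from failure.
2. Reword failure as loss or removal of the implant for any reason, mobility, or persistent pain or neuropathy, using the qualifier already in success criterion 1. The documents do not say how long persistent is. The investigators should fix its meaning before data are analysed, so that expected post-operative pain after either the placement or the exposure surgery does not count by itself.
3. State that a failed, lost or removed implant is not a success.
4. Reconcile the assessment visits under Clinical measurements with those in Appendix A.

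The cost is a small wording change, plus a note in the existing adverse-event entry on whether pain or neuropathy is still present. Adverse events are already scheduled from V2 to V10, so no visit, scale or radiograph is added. One limitation remains: pain first seen at V10 cannot be classed as persistent and should be listed separately.
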